Title	Systane Ultra Preservative Free Lubricant Eye Drops
Protocol Numbers	DEU894-I001
Study Sponsor	Alcon Research LLC [name]
Study Design	Post-Market, multicenter, non-comparative, single arm, open-label, prospective clinical study
Study Duration	The overall study duration (first subject screened to last subject's final study visit) is expected to be approximately 2 months.
Study Centers	Approximately 5 sites outside the US, where the product is commercially available.
Objectives	The objective of this post-market clinical follow-up (PMCF) study is to assess the performance and safety of Systane Ultra Preservative-Free (PF) in subjects experiencing dry eye symptoms (Group 1) and contact lens (CL) wearers experiencing discomfort due to CL-related dryness (Group 2).
Number of Subjects	54 evaluable subjects (27 per group)
Inclusion / Exclusion Criteria	
Subjects will be eligible to participate in the study if all of the following conditions exist:
 
 1. Subject must be at least 18 years of age. 2. Subject must be able to understand and sign an IRB/IEC approved informed consent form. 3. Subject must be willing and able to attend all study visits as required per protocol. 4. Subject with mild to moderate dry eye (Impact of Dry Eye on Everyday Life - Symptom Bother [IDEEL-SB] >16-64).^a 5. Subject with CL-related dry eye symptoms (Contact Lens Dry Eye Questionnaire [CLDEQ-8] ≥12).^b 6. Subject with a comfortable wear time with habitual contact lenses, which is less than the total wear time by at least 3 hours.^b 7. Subject must be willing to discontinue use of all habitual artificial tear supplements and use only the study device as directed for the entire study duration. 8. Subject using cyclosporine or other topical dry eye medications must be on a stable dosing regimen for ≥60 days prior to enrollment. 
^a Assessed in Group 1 only (subjects with mild to moderate dry eye) ^b Assessed in Group 2 only (subjects with end of day CL-related dryness)
 
Subjects will be excluded from participation in the study if any of the following conditions exist:
 
 1. Has suffered any ocular injury to either eye in the past 3 months prior to screening. 2. Has undergone any other ocular surgery (including intraocular surgery) within the past 6 months or has any ocular surgery planned during the study. 3. Employee or family member of Investigators or Alcon. 4. Currently enrolled in any clinical trial. 5. Use of any systemic medication known to cause dry eye (e.g., anti-histamine, anti-depressants, anti-psychotics, benzodiazepines, etc.) for less than 1 month before the Screening visit. If subject was on a stable regimen for at least a month prior to the Screening visit, the dosing regimen must not have changed for the duration of their participation in this study. In addition, subjects who did not currently use any of these medications could not start a regimen while participating in the study.

[figure not shown]
Study Device	Systane Ultra PF Lubricant Eye Drops
Comparator	N/A
Endpoints	
Primary effectiveness endpoints:
 
 • Group 1: Dry eye questionnaire via IDEEL-SB at entry and at Visit 3 • Group 2: Dry eye questionnaire via CLDEQ-8 at entry and at Visit 3 
[REDACTED]
 
[REDACTED]
 
Safety endpoints:
 
 • Biomicroscopy findings (include corneal staining) • Best corrected visual acuity (BCVA) • Adverse events (AEs) • Device deficiencies
Statistical Methods	
Statistical analyses will be presented by group (Group 1: subjects with mild to moderate dry eye; Group 2: subjects with end of day CL-related dryness). There is no statistical hypothesis for the endpoints in this study.
 
Appropriate descriptive statistics will be computed and presented for all categorical and continuous endpoints. A full description of statistical methods will be presented in the Statistical Analysis Plan.
 
 • For categorical variables, the number and percentage of subjects/eyes within each category of interest will be presented. • For continuous variables, the number of subjects/eyes with non-missing data, mean, standard deviation, range, median, minimum, and maximum will be presented. • There will be no imputation for missing data. 
All visual acuity results will be presented in logarithm of the minimum angle of resolution (logMAR) scale after applying appropriate transformations/conversions.

ABBREVIATIONS

Abbreviation	Definition
ADE	Adverse device effect
AE	Adverse event
ATP	Artificial tear products
BCVA	Best corrected visual acuity
CFR	Code of Federal Regulations
CL	Contact lens
CLDEQ-8	Contact Lens Dry Eye Questionnaire
CRF	Case report form
DED	Dry eye disease
EDC	Electronic data capture
eCRF	Electronic case report form
EU	European Union
FAS	Full analysis set population
FDA	Food and Drug Administration
GCP	Good Clinical Practice
GPCMS	Global Product Complaint Management System
HIPAA	Health Insurance Portability and Accountability Act of 1996
HP	Hydroxypropyl
ICF	Informed consent form
ICH	International Conference on Harmonization
IDEEL-SB	Impact of Dry Eye on Everyday Life - Symptom Bother
IEC	Independent Ethics Committee
IRB	Institutional Review Board
logMAR	Logarithm of the minimum angle of resolution
NaF1	Sodium fluorescein
████████	████████
OD, OS	Oculus dexter, Oculus sinister
PEG	Polyethylene glycol
PF	Preservative Free
PG	Propylene glycol
PHI	Protected Health Information
PI	Principal Investigator
PMCF	Post-market clinical follow-up
PP	Per-protocol population
QID	Four times a day
SADE	Serious adverse device effect
SAE	Serious adverse event
SOP	Standard operating procedures
US	United States

1.3.2 Global Medical Safety

Medical safety oversight will be provided by Alcon Global Medical Safety Representatives.

1.3.3 Statistician

Biostatistical analysis will be provided by the ICON Clinical Research Biostatistics group.

2 INTRODUCTION / BACKGROUND AND RATIONALE

Dry eye disease (DED) is a common ocular disorder, which affects many individuals worldwide. The prevalence of DED with/without symptoms ranges from 5% to 50%; and based on signs alone, up to 75%.¹

DED is characterized by a loss of homeostasis of the tear film resulting in ocular symptoms of discomfort, irritation, and visual disturbance, all of which significantly impact the patients' social and occupational quality of life.^{2,3} Tear film insufficiency may be the result of inadequate aqueous tear production by the main and accessory lacrimal glands, excessive evaporation of the tears from the ocular surface, or a combination of both.²

Common factors associated with DED include elder age, female gender, and the presence of autoimmune disease. DED is also reported in younger and pediatric populations.^{4,5} Other modifiable factors that can contribute to DED include the use of computers and digital devices, the use of heating, ventilation, and air conditioning systems, diet and lifestyle.⁴

Use of contact lens is also one of the reasons of DED, about 40% of contact lens wearers report dry eye symptoms.⁶

While management of DED depends on the severity of symptoms and signs, use of artificial tear products (ATPs) that replace or supplement the deficient natural tear film is the mainstay treatment option.⁷

Systane Ultra (polyethylene glycol [PEG]/propylene glycol [PG] with hydroxypropyl [HP] guar) has been shown to effectively alleviate signs and symptoms of dry eye, including conjunctival and cornea surface staining as well as patient-reported scores for treatment effectiveness and inconvenience. PEG/PG with HP guar has been shown to improve DED symptoms associated with cataract surgery, environmental conditions, and contact lens usage. Clinically, PEG/PG with HP guar lubricant eye drops have been shown to enhance tear film stability, visual function, comfort with contact lens wear, and improve visual acuity in patients with DED.⁸

Systane Ultra Preservative Free (PF) are eye drops formulated without preservatives.

This post-market clinical follow-up (PMCF) study aims to generate scientific evidence to address safety, performance, and clinical benefits of Systane Ultra PF in subjects with DED and contact lens (CL) wearers experiencing discomfort due to CL-related dryness.

3 STUDY DEVICE DESCRIPTION

Study device description is presented in Table 1.

Table 1. Study Device

Country	CANADA	
Product	SYSTANE™ ULTRA Lubricant Eye Drops Preservative Free	SYSTANE™ ULTRA Lubricant Eye Drops Preservative Free
Supply Type – Packaging and Labelling	Supplied in sterile single-use plastic vials containing 0.5 mL	Supplied in plastic bottles containing fill sizes of 3 mL or 10 mL.
Per Instructions for Use / Package Insert	Uses: For the temporary relief of burning and irritation due to dryness of the eye	SYSTANE™ ULTRA Lubricant Eye Drops Preservative Free is indicated for the temporary relief of burning and irritation due to dryness of the eye. SYSTANE™ ULTRA Lubricant Eye Drops Preservative Free may be used to lubricate and rewet daily, extended wear and disposable silicone hydrogel and soft (hydrophilic) contact lenses. SYSTANE™ ULTRA Lubricant Eye Drops Preservative Free moistens your contact lenses, reduces discomfort with contact lens wear, and helps to remove particulate material that may cause irritation and/or discomfort.
Storage Conditions	Store at room temperature	Do not store above 30°C

Country	AUSTRALIA / NEW ZEALAND	
Product	SYSTANE™ ULTRA UD Lubricant Eye Drops	SYSTANE™ ULTRA Lubricant Eye Drops
Supply Type – Packaging and Labelling	Supplied in sterile single-use plastic vials containing, 0.5 mL (packaged in multiples of 5 vials or more).	Supplied in plastic bottles containing fill sizes of 3 mL or 10 mL.
Per Instructions for Use / Package Insert	USES (Indications): SYSTANE™ ULTRA UD Lubricant Eye Drops is a dry eye therapy for the temporary relief of burning and irritation due to dryness of the eye. DIRECTIONS: SYSTANE™ ULTRA UD Lubricant Eye Drops may be used as needed throughout the day. May be used to treat dry eye associated with contact lens usage by instilling drops prior to inserting contact lenses and after the removal of contact lenses. Twist off the top of the single dose vial, place drops on the eye and blink. Discard the vial after use.	SYSTANE™ ULTRA Lubricant Eye Drops is intended for use by consumers for the temporary relief of burning and irritation due to dryness of the eye. SYSTANE™ ULTRA Lubricant Eye Drops is also intended for consumers wearing soft (hydrophilic) and silicone hydrogel contact lenses, including daily, extended wear, and disposable lenses.
Storage Conditions	Store below 30°C	Do not store above 30°C

4 PREPARATION/HANDLING/STORAGE/ACCOUNTABILITY

The study device should be handled as per the instruction for use.

Subjects will be asked to return the study device at Visit 3. Sites will account for the return of the study device accordingly, and are expected to dispose/destroy the study device per the standard practice.

5 STUDY OBJECTIVES

The objective of this PMCF study is to assess the performance and safety of Systane Ultra PF in subjects experiencing dry eye symptoms (Group 1) and CL wearers experiencing discomfort due to CL-related dryness (Group 2).

6 STUDY DESIGN

6.1 Overview of Study Design

This is a post-market, multicenter, non-comparative, open-label, prospective clinical study.

The study will be conducted outside the US, where the Systane Ultra PF is commercially available, in clinical sites known to routinely manage subjects with DED and CL wearers. The overall study duration (first subject screened to last subject's final study visit) is expected to be approximately 2 months.

Subjects will be enrolled into the study after signing the informed consent form (ICF).

Subjects who meet all the inclusion criteria and none of the exclusion criteria will initiate treatment with Systane Ultra PF. Eligible study participants (Group 1 and Group 2) will receive the first dose of Systane Ultra PF at the Screening/Baseline visit and will be required to self-administer Systane Ultra PF four times daily up to Visit 3. The dose selected in this study is the dose approved for Systane Ultra PF for the management of DED.

[figure not shown]
Subjects will participate in the study for approximately 30 days, with a phone call scheduled on Day 15 ± 2 (Visit 2) and a follow-up visit scheduled on Day 30 ± 2 (Visit 3). Subjects may have unscheduled visits if deemed necessary per the Investigator's judgment.

Subjects will be asked to complete patient questionnaires on Day 1 and at Visit 3 (Impact of Dry Eye on Everyday Life - Symptom Bother [IDEEL-SB] or Contact Lens Dry Eye Questionnaire [CLDEQ-8] and Comfortable Wear Time questions). In addition, the subjects will be instructed to document Systane Ultra PF dosing information on a daily basis using a subject diary.

A summary of the study design is shown in Figure 1. Study assessments are shown in the Schedule of Assessments (Table 4).

The study will enroll 68 subjects with the objective of 54 subjects completing treatment (27 in Group 1 and 27 in Group 2).

Figure 1. Overall Study Design

CL: Contact lens; QID: Four times a day.

Systane Ultra Preservative-free will be dispensed at Screening/Baseline visit. Subjects will be expected to attend one additional visit at Day 30 (± 2 days) after screening and a telephone call visit at Day 15 (± 2 days).

6.2 Anticipated Duration of the Clinical Investigation

The anticipated duration of the clinical trial is approximately 2 months. The anticipated number of clinical sites is up to 5. This will result in an accrual rate of 6.8 subjects per site per month.

6.3 Effectiveness and Safety Endpoints

6.3.1 Primary Effectiveness Endpoint

- Group 1: Dry eye questionnaire via IDEEL-SB at entry and at Visit 3
- Group 2: Dry eye questionnaire via CLDEQ-8 at entry and at Visit 3

6.3.3 Safety Endpoints

- Biomicroscopy findings (include corneal staining)
- Best corrected visual acuity (BCVA)

- Adverse events (AEs)
- Device deficiencies

6.4 Study Population

The study population consists of adult male and female subjects (≥ 18 years old) with mild to moderate dry eye disease and CL wearers who experience discomfort due to CL related dryness. Subjects will be recruited from clinical sites outside the US, where Systane Ultra PF is commercially available.

6.4.1 Sample Size

The study will recruit 68 subjects with a target to complete 54 evaluable subjects (27 in Group 1 and 27 in Group 2).

With a sample size of 54, a two-sided 95% confidence interval for a single proportion will extend 0.060 from the observed proportion when the expected proportion is 0.0543 (AEs).

Table 2 presents the precision for various rates of categorical outcomes.

Table 2. Precision for Various Percentages

Sample Size	Precision (%) for Various Rates of Outcomes			
	5%	10%	25%	50%
27	8.22%	11.32%	16.33%	18.86%
54	5.81%	8.00%	11.55%	13.34%

Precision calculated according to a simple asymptotic formula for a 2-sided 95% confidence interval for a proportion based on the normal approximation of the binomial distribution.⁹

6.4.2 Subject Recruitment

Subjects will be recruited from the clinical practices of the participating Investigators and surrounding metropolitan areas. Additional advertisement is not expected to be required.

6.4.3 Prior and Concomitant Therapy or Medications

Concomitant Medications

Targeted concomitant medications (see Section 7.3.2) must be recorded in source documents and on the appropriate electronic case report form (eCRF).

Prohibited Concomitant Medications

For subjects who meet all of the inclusion criteria and none of the exclusion criteria, the initiation

of systemic medications known to cause dry eye (e.g., anti-histamine, anti-depressants, anti-psychotics, benzodiazepines, etc.) or known to treat dry eye (e.g., Restasis, Xiidra, Cequa) is not permitted during the study.

Rescue Medicine

Not applicable.

6.4.4 *Inclusion Criteria*

Subjects will be eligible to participate in the study if **all** of the following conditions exist:

1. Subject must be at least 18 years of age.
2. Subject must be able to understand and sign an IRB/IEC approved informed consent form.
3. Subject must be willing and able to attend all study visits as required per protocol.
4. Subject with mild to moderate dry eye (IDEEL-SB >16-64).^a
5. Subject with CL-related dry eye symptoms (CLDEQ-8 ≥12).^b
6. Subject with a comfortable wear time with habitual contact lenses, which is less than the total wear time by at least 3 hours.^b
7. Subject must be willing to discontinue use of all habitual artificial tear supplements and use only the study device as directed for the entire study duration.
8. Subject using cyclosporine or other topical dry eye medications must be on a stable dosing regimen for ≥60 days prior to enrollment.

^a Assessed in Group 1 only (subjects with mild to moderate dry eye)

^b Assessed in Group 2 only (subjects with end of day CL-related dryness)

6.4.5 *Exclusion Criteria*

Subjects will be excluded from participation in the study if any of the following conditions exist:

1. Has suffered any ocular injury to either eye in the past 3 months prior to screening.
2. Has undergone any other ocular surgery (including intraocular surgery) within the past 6 months or has any ocular surgery planned during the study.
3. Employee or family member of Investigators or Alcon.

4. Currently enrolled in any clinical trial.
5. Use of any systemic medication known to cause dry eye (e.g., anti-histamine, anti-depressants, anti-psychotics, benzodiazepines, etc.) for less than 1 month before the Screening visit. If subject was on a stable regimen for at least a month prior to the Screening visit, the dosing regimen must not have changed for the duration of their participation in this study. In addition, subjects who did not currently use any of these medications could not start a regimen while participating in the study.

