17.2.2 CLDEQ-8 Questionnaire

CONTACT LENS QUESTIONNAIRE-8 (CLDEQ-8)

1. Questions about EYE DISCOMFORT:

a. During a typical day in the past 2 weeks, **how often** did your eyes feel discomfort while wearing your contact lenses?

0 Never
1 Rarely
2 Sometimes
3 Frequently
4 Constantly

When your eyes felt discomfort with your contact lenses, **how intense was this feeling of discomfort...**

b. At the end of your wearing time?

Never	Not at All		Very	Intense
0	1	2	3	4
0	1	2	3	4

2. Questions about EYE DRYNESS:

a. During a typical day in the past 2 weeks, **how often** did your eyes feel dry?

0 Never
1 Rarely
2 Sometimes
3 Frequently
4 Constantly

When your eyes felt dry, **how intense was this feeling of dryness...**

b. At the end of your wearing time?

Never	Not at All		Very	Intense
0	1	2	3	4
0	1	2	3	4

3. Questions about CHANGEABLE, BLURRY VISION:

a. During a typical day in the past 2 weeks, **how often** did your vision change between clear and blurry or foggy while wearing your contact lenses?

0 Never
1 Rarely
2 Sometimes
3 Frequently
4 Constantly

When your vision was blurry, **how noticeable was the changeable, blurry, or foggy vision ...**

b. At the end of your wearing time?

Never	Not at All		Very	Intense
0	1	2	3	4
0	1	2	3	4

4. Question about CLOSING YOUR EYES:

During a typical day in the past 2 weeks, **how often** did your eyes **bother you so much that you wanted to close them?**

[figure not shown]
0 Never
1 Rarely
2 Sometimes
3 Frequently
4 Constantly

5. Question about REMOVING YOUR LENSES:

How often during the past 2 weeks, did your eyes **bother you so much** while wearing your contact lenses that you felt as if you needed to stop whatever you were doing and **take out your contact lenses?**

1 Never
2 Less than once a week
3 Weekly
4 Several times a week
5 Daily
6 Several times a day

Copyright © Trustees of Indiana University, 2009, all rights reserved

Alcon

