5.1. Efficacy Endpoints

PRIMARY EFFECTIVENESS ENDPOINT:

The primary effectiveness endpoint is:

- Group 1: Dry eye (DE) questionnaire via IDEEL-SB at Baseline and at Visit 3
- Group 2: DE questionnaire via CLDEQ-8 at Baseline and at Visit 3

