5.3. Statistical Methods for Efficacy Analyses

5.3.1. Primary Effectiveness

Group 1:

DES will be assessed using the IDEEL-SB questionnaire (see [Appendix 13.2](#)) at the Screening/Baseline visit (Day 1) before Systane Ultra PF use, and at Visit 3 (and at unscheduled and at early exit visits, as necessary).

The primary effectiveness endpoint is the IDEEL-SB score. The IDEEL-SB score is calculated by the mean value of the non-missing item scores multiplied by 25, with a higher score indicating greater satisfaction and less treatment-related bother.

The primary effectiveness endpoint will be summarized as a continuous variable at each analysis visit (Baseline and Visit 3). The mean IDEEL-SB score will be presented together with the corresponding 95% CI.

Group 2:

CL symptoms will be assessed using the CLDEQ-8 questionnaire (see [Appendix 13.3](#)) at the Screening/Baseline visit (Day 1) before Systane Ultra PF use, and at Visit 3 (and at unscheduled and at early exit visit, as necessary).

[figure not shown]
The primary effectiveness endpoint is the CLDEQ-8 score. The CLDEQ-8 score is calculated by the sum of the non-missing item questions.

The primary effectiveness endpoint will be summarized as a continuous variable at each analysis visit (Baseline and Visit 3). The mean CLDEQ-8 score will be presented together with the corresponding 95% CI. [REDACTED]

Derivations:

- IDEEL-SB score = (Sum of (Item 1,..., Item 20) / n) x 25, where n = number of items with non-missing answer.
- CLDEQ-8 score = Sum of (Question 1,..., Question 8).

A large rectangular area of the page is completely blacked out, indicating that the original content has been redacted.

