7.1.2. Contact Lenses

For Group 2, information on type of contact lenses used will be listed.

8. Sample Size and Power Calculations

The study will recruit 68 subjects with a target to complete 54 evaluable subjects (27 in Group 1 and 27 in Group 2).

With a sample size of 54, a two-sided 95% CI for a single proportion will extend 0.060 from the observed proportion when the expected proportion is 0.0543 (AEs). [Table 3](#) presents the precision for various rates of categorical outcomes.

Table 3: Precision for Various Percentages

Sample Size	Precision (%) for Various Rates of Outcomes			
	5%	10%	25%	50%
27	8.22%	11.32%	16.33%	18.86%
54	5.81%	8.00%	11.55%	13.34%

Precision calculated according to a simple asymptotic formula for a 2-sided 95% CI for a proportion based on the normal approximation of the binomial distribution.

9. Quality Control and Version Control

[figure not shown]
The Statistical Analyst will direct the project team to apply quality control and data validation programming to ensure consistency and accuracy of the statistical analysis datasets, statistical analyses, and associated output, according to ICON standard operating procedures [REDACTED]

[REDACTED] review involves, but is not limited to the following: generation of QC statistics, checking calculations of derived variables, confirmation of analytic cohort, examination of the SAS® LOG or equivalent, confirmation of statistical validity, and consistency of output across tables, listings, and figures.

ICON plc will designate the initial version of the SAP approved by the Sponsor and ICON plc as Version 1.0. ICON plc will document any changes made to the SAP in a new version and the version number updated. ICON plc may complete revisions to SAP attachments without requiring additional revisions and approval to the SAP.

10. References

- [4] Friedman NJ. Impact of dry eye disease and treatment on quality of life. *Curr Opin Ophthalmol*. 2010;21(4):310–316.

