12.3. CLDEQ-8 Questionnaire

CONTACT LENS QUESTIONNAIRE-8 (CLDEQ-8)

1. Questions about **EYE DISCOMFORT**:

a. During a typical day in the past 2 weeks, **how often** did your eyes feel discomfort while wearing your contact lenses?

- 0** Never
- 1** Rarely
- 2** Sometimes
- 3** Frequently
- 4** Constantly

When your eyes felt discomfort with your contact lenses, **how intense was this feeling of discomfort...**

b. At the end of your wearing time?

Never	Not at All	Very			
have it	Intense	Intense			
0	1	2	3	4	5

2. Questions about **EYE DRYNESS**:

a. During a typical day in the past 2 weeks, **how often** did your eyes feel dry?

- 0** Never
- 1** Rarely
- 2** Sometimes
- 3** Frequently
- 4** Constantly

When your eyes felt dry, **how intense was this feeling of dryness...**

b. At the end of your wearing time?

Never	Not at All	Very			
have it	Intense	Intense			
0	1	2	3	4	5

3. Questions about **CHANGEABLE, BLURRY VISION**:

a. During a typical day in the past 2 weeks, **how often** did your vision change between clear and blurry or foggy while wearing your contact lenses?

- 0** Never
- 1** Rarely
- 2** Sometimes
- 3** Frequently
- 4** Constantly

When your vision was blurry, **how noticeable was the changeable, blurry, or foggy vision ...**

b. At the end of your wearing time?

Never	Not at All	Very			
have it	Intense	Intense			
0	1	2	3	4	5

4. Question about **CLOSING YOUR EYES**:

During a typical day in the past 2 weeks, **how often** did your eyes bother you so much that you wanted to close them?

- 0** Never
- 1** Rarely
- 2** Sometimes
- 3** Frequently
- 4** Constantly

[figure not shown]
5. Question about **REMOVING YOUR LENSES**:

How often during the past 2 weeks, did your eyes bother you so much while wearing your contact lenses that you felt as if you needed to stop whatever you were doing and **take out your contact lenses**?

- 1** Never
- 2** Less than once a week
- 3** Weekly
- 4** Several times a week
- 5** Daily
- 6** Several times a day

Copyright© Trustees of Indiana University, 2009, all rights reserved

Patient/Subject #: _____
Date: ____/____/____ Time: _____

13. Tables, Listings, and Figures

A separate document contains the shells to be employed in this study.

Table 14.1.1.1.1: Subject Disposition

Table 14.1.1.1.2: Subject Disposition by Site

Table 14.1.2.1.1: Major Protocol Deviations – FAS

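### Group 2 lenses are not held constant, and lens data are not visibly used to qualify the Visit 3 CLDEQ-8, so a completer who stops wearing lenses can appear improved

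*Protocol*

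**What the plan says.** Group 2 enters on two lens-related criteria in Protocol 6.4.4: a symptom score ("Subject with CL-related dry eye symptoms (CLDEQ-8 ≥12") and a wear-time gap ("Subject with a comfortable wear time with habitual contact lenses, which is less than the total wear time by at least 3 hours"). Both describe the subject at screening.

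For the weeks that follow, the plan restricts other things. Criterion 7 reads "Subject must be willing to discontinue use of all habitual artificial tear supplements and use only the study device as directed for the entire study". Criterion 8 asks for a stable regimen of topical dry eye drugs before enrolment. Exclusion 5 in Protocol 6.4.5 requires systemic drugs that cause dry eye to stay unchanged. The prohibited list in Protocol 6.4.3 covers medications only, and the exit criteria in 6.4.6 mention neither a change of lens nor stopping lens wear.

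SAP 5.1 gives the primary endpoint as "Group 2: DE questionnaire via CLDEQ-8 at Baseline and at Visit 3". SAP 5.3.1 gives the scoring: "The CLDEQ-8 score is calculated by the sum of the non-missing item questions". The completeness rule in SAP 5.4 (at least 10 of 20 items) covers IDEEL-SB only.

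Some lens information is collected. Protocol 6.1 has subjects answer Comfortable Wear Time questions on Day 1 and at Visit 3. SAP 7.1.2 states: "For Group 2, information on type of contact lenses used will be listed".

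**The concern.** CLDEQ-8 looks back two weeks, and most of it has meaning only for someone who wore lenses in that time. Item 1a, for example, asks how often "did your eyes feel discomfort while wearing your contact lenses". A subject who gave up lenses before the recall period has no lens discomfort to report, and the form offers nothing better suited than the lowest answer or a blank. Under the stated scoring, both lower the total, and a lower total means fewer symptoms.

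If the subject gave up lenses because the drop did not help, a poor outcome is recorded as a good one. The study has a single arm, so no control group would show the same artefact and cancel it. It would appear directly as a lower Visit 3 mean beside the baseline mean on a primary endpoint.

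**Working it through.** **Inputs.** Item wording and limits come from SAP 12.3. The intensity scale in Protocol 17.2.2 is not cleanly legible in the copy reviewed, so the SAP scale is used; the floor is the same either way. The entry threshold of 12 is in Protocol 6.4.4 and the 27 evaluable Group 2 subjects are in Protocol 6.4.1. The plan states no CLDEQ-8 range, standard deviation or expected change, so there is no figure of its own to reproduce here.

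**Step 1: range of the form.**
- Items 1a, 2a, 3a and 4 run 0–4: 4 × 4 = 16.
- Items 1b, 2b and 3b run 0–5: 3 × 5 = 15.
- Item 5 runs 1–6.
- Maximum: 16 + 15 + 6 = 37. Minimum of a complete form: 0 + 0 + 1 = 1.

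**Step 2: which items need lenses.** Items 1a, 3a and 5 confine the question to time with lenses in. Items 1b, 2b and 3b ask about the end of wearing time. These six carry 4 + 4 + 6 + 5 + 5 + 5 = 29 of the 37 points. Item 2a (how often "did your eyes feel dry") and item 4 (wanting to close the eyes) are not worded as depending on lenses, and together run 0–8.

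**Step 3: score of a completer who has stopped wearing lenses.**
- Six lens items at the lowest option: 0 × 5 + 1 = 1, plus 0–8 from items 2a and 4, gives **1–9**.
- Six lens items blank, sum of non-missing items: **0–8**.

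Both ranges lie wholly below 12. Even with the worst answers on dryness and eye closing, such a subject scores below the entry threshold.

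**Step 4: fall from entry, and shift in a mean of 27.** The shift is fall ÷ 27 per subject, compared with that subject staying at the entry score.

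| Entry score | Lens items | Fall | Shift in mean |
|---|---|---|---|
| 12 (threshold) | lowest option | 12 − 9 = 3 to 12 − 1 = 11 | 0.11 to 0.41 |
| 12 (threshold) | blank | 12 − 8 = 4 to 12 − 0 = 12 | 0.15 to 0.44 |
| 20 (assumed) | lowest option | 20 − 9 = 11 to 20 − 1 = 19 | 0.41 to 0.70 |

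If three subjects did this (an assumption), the lowest-option shift from 12 would be 3 × 3/27 = 0.33 to 3 × 11/27 = 1.22.

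**Step 5: scale.** The 95% half-width for a mean of 27 is t(0.975, 26) × SD/√27. At assumed SDs of 4, 6 and 8 this is 1.58, 2.37 and 3.16. One such subject is small against that width. Three at the upper end of the range are not negligible, and every shift runs in the same direction.

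**The case against.** A reader might infer that nothing checks lens wear. The documents do not support that. Wear-time questions are asked at both clinic visits, lens type is listed, CLDEQ-8 forms are listed by subject, and Visit 2 includes a compliance call, though its content is not given. Text after the CLDEQ-8 summary in SAP 5.3.1 is redacted, as are rows in both schedules. Exclusions from the per-protocol set sit in a Protocol Deviation Criteria Form that is not in the documents. What stands is narrower: the unredacted entry criteria contain no lens-constancy requirement, and no visible rule links the lens data to the score.

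A reader might also infer that anyone who stops lenses must score a near-maximal gain. That would require items 2a and 4 at zero as well, and persistent dryness can keep them high. From an entry score of 12 the fall can be as small as 3 points.

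Nor can a switch to a different lens be assumed to flatter the product. The documents give neither size nor direction for that effect.

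A subject for whom the drop fails may leave the study, since lack of efficacy is an exit reason in Protocol 6.4.6. An early-exit form completed outside Days 28–32 would not fall in the Visit 3 window of SAP Table 2. The artefact therefore needs someone who stops lenses and still completes. This limits how often it can occur but does not remove it.

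Finally, there is no hypothesis or success threshold (Protocol 8.2, SAP 5.2), and a post-market study may reasonably reflect ordinary use. No pass/fail decision turns on the shift. The Group 2 mean with its confidence interval is still the main evidence of performance in lens wearers.

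**Conclusion.** The point holds in a limited form. No visible text requires Group 2 to keep the same lenses or lens care, and the lens data collected are not visibly used to qualify the Visit 3 CLDEQ-8. With no minimum-item rule, a completer who has stopped lens wear, and who gives the lens items the lowest answer or leaves them blank, can appear improved from any eligible entry score. The effect per subject on a mean of 27 is 0.11 to 0.44 points from the threshold of 12, and up to 0.70 from an assumed entry score of 20.

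This rests on three assumptions: the subject completes Visit 3, answers the six items in one of those two ways, and 27 Group 2 subjects are analysed. How many subjects would do this cannot be derived. No CLDEQ-8 change score is visible, so the effect would be seen as a lower Visit 3 mean. It is worth correcting because the scoring, followed as written, can present abandonment of lenses as benefit on a primary endpoint.

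**What to change.** 1. **Protocol 6.4.4, Group 2:** add willingness not to change habitual lens type or care solution during the study. Do not oblige anyone to continue wearing lenses.
2. **eCRF, Visits 1 and 3:** record lens type, care solution and the number of days lenses were worn in the two-week recall period.
3. **SAP 5.3.1 and 5.4:** state that no valid CLDEQ-8 total is formed when the lens-dependent items are blank or no lenses were worn in the recall period. Flag complete forms from subjects who stopped or changed lenses.
4. **SAP reporting:** give the number who stopped or changed lenses beside the Group 2 mean, as an outcome. Show the Visit 3 mean twice: once with every complete form as recorded, including those from non-wearers, and once without the flagged scores.

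Stoppers should not simply be removed as per-protocol deviations. If they stopped because the drop did not help, removal would hide failures and still favour the product.

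The cost is one criterion, two or three eCRF fields at existing visits and a short SAP rule. The downside is a few flagged or missing Visit 3 scores.
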